Functional Anterior Temporal Lobectomy via Minicraniotomy as a Novel Surgical Therapy for Temporal Lobe Epilepsy: A Randomized, Controlled Trial

BACKGROUND: Anterior temporal lobectomy (ATL) is the most effective therapy for drug-resistant temporal lobe epilepsy (TLE). However, patients are reluctant to choose the surgery for the fear of risks after large frontotemporal craniotomy. Epileptologists also have cautious attitude towards referring patients with TLE for ATL due to surgical related trauma. As a new surgical approach, functional anterior temporal lobectomy (FATL) is a minimally invasive therapy for well addressing above concerns.

OBJECTIVE: To compare the surgical procedure, safety, and efficacy of FATL for TLE with ATL.

METHODS: This was a single-center, prospective, randomized controlled trial. A total of 120 patients aged between 18 and 60 years with drug-resistant TLE will be enrolled for at least 3 years. Patients will be randomly assigned to receive either FATL (n = 60) or ATL (n = 60). Primary outcomes include surgery duration, intraoperative blood loss, length of skin incision, size of bone flap, postoperative hospital stay, cosmetic appearance of the wound, and complications at the 1-year follow-up after surgery. Secondary outcomes are seizure outcomes, quality of life evaluated by the epilepsy-specific Quality of Life in Epilepsy Inventory-89, and neuropsychological outcomes.

EXPECTED OUTCOMES: We expect to find more favorable outcomes of FATL for TLE compared to ATL, while seizure outcomes following FATL are expected to be similar to ATL.

DISCUSSION: The surgical procedure, safety, and efficacy of FATL for TLE will be verified in this trial. FATL is a less-invasive approach. As a level 1 evidence, FATL could be strongly recommended to treat TLE.

SHORT TITLE: Functional anterior temporal lobectomy for TLE

KEY WORDS: Anterior temporal lobectomy, Functional anterior temporal lobectomy, Minicraniotomy, Randomized controlled trial, Temporal lobe epilepsy.

ABBREVIATIONS: ATL, anterior temporal lobectomy; eCREF, electronic case report forms; EEG, electroencephalogram; FLAIR, fluid-attenuated inversion recovery; FATL, functional anterior temporal lobectomy; ICF, informed consent form; IQ, intelligence quotient; MRI, magnetic resonance imaging; PET, positron emission computed tomography; TLE, temporal lobe epilepsy.

GENERAL INFORMATION

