For addressing the above concerns, we modify the surgical approach. Functional anterior temporal lobectomy (FATL) via minicraniotomy is established as an alternative. To date, this open surgery for TLE has not been reported. The surgical procedure, safety, and efficacy of FATL must be verified. Therefore, we present a protocol for the MASET-TLE trial. This is the first study to evaluate the clinical outcomes of FATL as a novel surgical approach for TLE.

STUDY GOALS AND OBJECTIVES

Hypothesis

As a minimally invasive procedure, the overall hypothesis is that patients with TLE will benefit from FATL, with seizure control and neuropsychological outcomes no less than standard ATL whereas complications and cosmetic appearance superior to ATL. Therefore, the goal of this study was to measure the surgical technique, safety, and efficacy of FATL compared to ATL at the department of neurosurgery in our hospital.

Primary Objective

- Minimally invasive outcomes: surgery duration, intraoperative blood loss, length of skin incision, bone flap size, and postoperative hospital stay.
- Complications and cosmetic appearance of the wound at the 1-year follow-up after epilepsy surgery.

Secondary Objectives

- Seizure outcomes were categorized according to the Engel and International League Against Epilepsy (ILAE) classifications.¹⁸ The actuarial seizure outcomes over time were evaluated using the Kaplan–Meier analysis.

- Quality of life is evaluated by the epilepsy-specific Quality of Life in Epilepsy Inventory-89 (QOLIE-89; range of scores, 0 to 100, with higher scores indicating better quality of life).¹⁹
- Neuropsychological outcomes were assessed according to the consensus reported by Brissart.²⁰

STUDY DESIGN

MISSET-TLE is a single-center, prospective, single-blinded, double-arm, randomized controlled trial. A total of 120 patients are planned to be recruited (60 patients per group). The anticipated completion date will be in July 2024. SPIRIT checklist is used when writing our report.²¹

Inclusion/Exclusion Criteria

Inclusion Criteria

- male or female aged between 18 and 60 years.
- drug-resistant TLE, with remaining seizures after two or more tolerated and appropriately chosen antiepileptic drugs for at least 1 year.
- monthly or more frequent seizures during the preceding year prior to the trial.
- full-scale intelligence quotient (IQ) more than 70, able to understand and complete the trial.
- signed informed consent.

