Patients will be assigned with computer-generated random numbers by an independent statistician. Randomization is stratified by sex, with separate permuted blocks for each sex. Allocations are concealed until participants' eligibility and identities are confirmed. Allocations are also sequentially numbered in a 1:1 ratio to either receive FATL (experimental group) or

ATL (control group). Assessors evaluating the outcomes will be blinded to treatment throughout the study. Blinding is maintained by having patients wear large hats during reviews to obscure skin incision and providing patients strict instructions not to reveal their treatment arm.

Surgical Intervention

FATL

Patients will be placed in the supine position with their head contralaterally rotated by 30°. The 3D model of the incision and bone flap will be printed prior to the surgery using the slicer software based on the MRI data. A slightly curve incision with a length of approximately 6 cm in the temporal region beginning from the zygomatic arch will be marked (Figure 2A). A temporal craniotomy via a small bone window with a diameter of about 3 cm will be performed (Figure 2B and C). From the temporal pole approximately 4-5 cm posteriorly, the temporal horn is opened by dissecting the middle temporal gyrus. The head of the temporal horn will be exposed. The amygdala will be resected. Then, the parahippocampal gyrus and the hippocampus will be resected en bloc. Temporal lobotomy is easy because of the large view following the removal of the mesial structures (Figure 2D and E). The lateral posterior temporal lobotomy was no more than 5 cm from the temporal pole. Finally, the temporal stem was divided to isolate the superior temporal gyrus.

ATL

Patients will be placed in the supine position with their head contralaterally rotated by 30°. A large frontotemporal craniotomy will be performed. A question mark-shaped incision with a length of 20-25 cm in the frontotemporal region beginning from the zygomatic arch will be marked (Figure 2F). The size of the bone flap is approximately 5 × 7 cm for exposure of the lateral temporal lobe (Figure 2G and H). ATL consists of a standard protocol including en bloc resection of the anterior 5 cm of the lateral temporal lobe, followed by the removal of mesial structures including the amygdala, parahippocampal gyrus, and the hippocampus (Figure 2I and J).

DISCUSSION

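### Seven unranked primary outcomes share one unadjusted P<0.05 with no success rule behind the planned superiority claim, and two of them are fixed by the operations themselves

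*Combined protocol and SAP*

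**What the plan says.** The abstract (Methods) states: "Primary outcomes include surgery duration, intraoperative blood loss, length of skin incision, size of bone flap, postoperative hospital stay, cosmetic appearance of the wound", and adds complications at the 1-year follow-up. The Primary Objective section repeats the same seven in two bullets, without ranking them: "Minimally invasive outcomes: surgery duration, intraoperative blood loss, length of skin incision, bone flap size, and postoperative hospital stay" and "Complications and cosmetic appearance of the wound at the 1-year follow-up after epilepsy surgery".

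Statistical Considerations bases the sample size on surgery duration alone (3.4 h against 3.0 h, 50 per group, 90% power, two-sided 0.05), raised to 120 patients for 20% attrition. It compares means by t-test and proportions by chi-squared or Fisher test, all at P<0.05. No lead outcome, hierarchy, co-primary rule or adjustment is given.

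The Surgical Intervention section sets two of the seven by design:
- FATL: "A slightly curve incision with a length of approximately 6 cm in the temporal region" and "a small bone window with a diameter of about 3 cm".
- ATL: "A question mark-shaped incision with a length of 20-25 cm" and a bone flap of about 5 × 7 cm.

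The Hypothesis section expects patients to benefit, "with seizure control and neuropsychological outcomes no less than standard ATL whereas complications and cosmetic appearance superior to ATL". Expected Outcomes of the Study promises level I evidence that FATL is superior, and the abstract's discussion says: "As a level 1 evidence, FATL could be strongly recommended to treat TLE".

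**The concern.** The intended conclusion is not tied to any result. Nothing says which of the seven outcomes, or how many, must favour FATL before superiority is claimed.

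The Hypothesis section places superiority in complications and cosmetic appearance, but the sample size rests on surgery duration. The Hypothesis wording could be read as requiring both of its named outcomes, but it does not say so.

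As written, the claim could rest on incision length and flap size, which differ because the operations were defined to differ. It could also rest on a single chance finding among the other five. Either way, a strong treatment recommendation could follow with no demonstrated benefit on complications or cosmetic appearance.

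**Working it through.** **1. The plan's own figure.** No SD is stated, so 50 per group cannot be reproduced from the stated inputs. Solving backwards with the noncentral t distribution, 90% power at 50 per arm and two-sided 0.05 needs a standardised difference d = 0.655. The implied SD is 0.4 / 0.655 = 0.61 h. The power figures for duration below use this value unless they say otherwise.

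**2. The two prescribed measures.**
- Incision: the smallest planned difference is 20 − 6 = 14 cm.
- Bone opening, taking the FATL window as circular: π × 1.5² = 7.07 cm² against 5 × 7 = 35 cm², a difference of 27.9 cm².
- With 60 operated per arm, 99% power at two-sided 0.05 needs d = 0.789. Power would fall below 99% only if the SD exceeded 14 / 0.789 = 17.7 cm, or 27.9 / 0.789 = 35.4 cm².
- The first SD is nearly three times the whole FATL incision, and the second is about the whole ATL flap. Significance is practically assured.

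**3. False positives among the other five.** These rates apply only if any one significant result counts as success. With k true, independent nulls, the chance of at least one false positive in FATL's favour is 1 − 0.975^k. The two-sided chance is 1 − 0.95^k.

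| True nulls (k) | In FATL's favour (nominal 2.5%) | Two-sided (nominal 5%) |
|---|---|---|
| 5 | 11.9% | 22.6% |
| 4 | 9.6% | 18.5% |
| 3 | 7.3% | 14.3% |
| 2 | 4.9% | 9.8% |

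The five outcomes are probably correlated. Simulating equicorrelated normal test statistics with all five nulls true gives about 10.5% and 9% in FATL's favour at correlations of 0.3 and 0.5, and 21% and 18% two-sided.

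**4. With Holm over the five.** Simulation with all nulls true and correlations of 0 / 0.3 / 0.5 gives 4.9% / 4.7% / 4.2% two-sided, and 2.5% / 2.3% / 2.1% in FATL's favour.

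**5. Power at Holm's strictest step (0.05 / 5 = 0.01).** This is a floor, because the threshold relaxes once another outcome passes.

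Surgery duration (noncentral t; the SDs of 0.5, 0.7 and 0.8 h are assumptions):

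| SD | n per arm | Power at 0.05 | Power at 0.01 |
|---|---|---|---|
| 0.61 h | 60 | 94% | 83% |
| 0.61 h | 50 | 90% | 74% |
| 0.5 h | 60 | 99% | 96% |
| 0.7 h | 60 | 87% | 70% |
| 0.8 h | 60 | 78% | 55% |

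Complications at 60 × 0.8 = 48 per arm (exact enumeration of the uncorrected chi-squared test; the documents give no rates, so those below are assumptions):

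| ATL vs FATL rate | Power at 0.05 | At 0.025 (Holm over two) | At 0.01 (Holm over five) |
|---|---|---|---|
| 20% vs 10% | 29% | 19% | 10% |
| 30% vs 15% | 43% | 31% | 20% |
| 40% vs 20% | 59% | 47% | 33% |

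**The case against.** - **The error rates presuppose a rule the plan does not state.** If success required all seven outcomes, or both outcomes named in the Hypothesis section, nothing would be inflated and no adjustment would be needed. That is correct. The established defect is the missing rule, and the inflation is one possible consequence of it. The documents do not adopt a stricter rule either.
- **Surgery duration is the lead outcome in practice, because it sets the sample size.** It is never designated so, and the superiority hypothesis does not mention it.
- **Independence does not strictly cap the one-direction rate.** This stands as a small point. With negative correlation the bound is 5 × 2.5% = 12.5%, not 11.9%.
- **Expected Outcomes also anticipates better neuropsychological results.** These are secondary, and the Hypothesis section expects them only to be no worse. Limiting superiority statements to primary outcomes that pass deals with this.
- **Holm over five weakens the two outcomes the hypothesis cares about.** This is fair: the strictest-step power for complications is 10%, 20% or 33%, against 19%, 31% or 47% if those two are tested first. Choosing that order in advance would be equally valid.
- **The change costs power or patients.** Also fair. Keeping 90% power for duration at 0.01 would need about 72 evaluable per arm (71 by normal approximation) against the planned 50.
- **Only assessors are blinded, so the surgical team sees outcomes as they occur.** True, and it affects who should decide the amendment. It does not remove the need for one.

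**Conclusion.** The concern holds and must be fixed before results by arm are examined. Three facts come directly from the text: seven unranked primary outcomes, one unadjusted threshold with no success rule, and two primary outcomes built into the operations. They rest on no assumption.

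The size of the error is conditional. If any one of the remaining five sufficed, the false-positive chance in FATL's favour would be roughly 9% to 12% with all five nulls true, or 4.9% to 9.6% with two to four true and independent, against 2.5%. If the two prescribed measures also counted, a positive result would be practically guaranteed whatever the clinical benefit.

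The power figures rest on a back-solved SD and on assumed SDs and complication rates, because the documents give none. Power for complications is low over the assumed range even without adjustment.

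**What to change.** 1. Report incision length and bone-flap size descriptively, as a record of the procedure delivered. Do not use them as primary outcomes or as evidence of superiority.
2. Test surgery duration, blood loss, hospital stay, cosmetic appearance and complications with Holm at familywise two-sided 0.05. The ordered P-values are compared with 0.01, 0.0125, 0.0167, 0.025 and 0.05, and no outcome acts as a gate. Run it once, after the last 1-year visit, because Holm needs all five P-values. The sponsor may instead pre-specify another order that controls the error, for example complications and cosmetic appearance first.
3. Limit superiority statements to the outcomes that pass. Claim superiority on complications or cosmetic appearance only if those pass.
4. Define one analysis variable for each outcome.
   - Complications: for example, any complication from surgery to the 1-year visit, yes or no, whatever its grade. The grading in Safety Considerations has no category for a complication that lasts over 3 months without affecting daily living. Counting only those present at 1 year would miss the minor ones, which by definition have resolved within 3 months.
   - Cosmetic appearance: one named scale at 1 year. The documents name none.
5. Recruitment began in September 2021, so make the change by dated amendment. It should be decided by people who have not seen outcome data by arm, and the amendment should say so.
6. Restate the power at the stricter threshold.

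The cost is an amendment and, if none is in use, the choice of a cosmetic scale. No extra patients or visits are needed if the lower power is accepted. For duration at the back-solved SD, that means 83% rather than 94% with 60 operated per arm, or 74% rather than 90% with 50, at the strictest step. Restoring 90% there would take about 72 evaluable per arm.

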Epilepsy surgery has proven to be very efficient for TLE and superior to medical therapy in two randomized controlled trials.^{4,5} Patients undergoing surgical therapy have a high seizure-free rate, ranging from 60% to 80 %, while the rate is less than 5% with medical treatment.⁶ Since surgical therapy of temporal lobe epilepsy and the technique of temporal lobectomy were firstly reported by Penfield in 1950s,^{7,8} anterior temporal lobectomy (ATL) is the most frequently used approach for TLE.⁹ For patients with TLE, Engel suggested that referral to ATL should be strongly considered.¹⁰ The decision analysis showed that ATL increased life expectancy and quality-adjusted life expectancy in patients with TLE compared with medical management.¹¹ Although complication rates after ATL have decreased dramatically over time,¹² complications remain an unavoidable consequence of this large frontotemporal craniotomy. ATL creates a large cavity due to temporal lobe resection, causing potential risks such as subdural collections, cerebrospinal fluid leakage, and brain shifts. Scar wound and muscular atrophy after frontotemporal craniotomy result in poor cosmetic appearance, hindering the usage of ATL. With advances in minimally invasive surgery, ATL has been modified to different surgical approaches for TLE.^{13,14} As a standard procedure, ATL still has excellent results compared with other approaches.¹⁴

However, ATL for TLE is underutilized worldwide by far. A nationwide survey in Sweden showed annual number of epilepsy surgery declined between 1991 and 2007 at a rate of 2.5 per year, suggesting neurologists have a cautious attitude towards epilepsy surgery.¹⁵ Similarly, the numbers for all surgical procedures except vagus nerve stimulation had decreased from

2000 to 2011 in United Kingdom.¹⁶ As well, the annual rate of ATL for TLE declined by >65% between 2006 and 2010.¹⁷ Reasons for the decline in ATL for TLE are unclear and speculative. One of the important factors may be that ATL is performed by large frontotemporal craniotomy, causing potential complications (e.g. poor cosmetic appearance, infection, neurological deficits, etc.). Fear of the risks after large craniotomy makes patients reluctant to choose ATL and epileptologists inactive to refer patients with TLE to surgical center.

For addressing the above concerns, we modify the surgical approach. Functional anterior temporal lobectomy (FATL) via minicraniotomy is established as an alternative. To date, this open surgery for TLE has not been reported. The surgical procedure, safety, and efficacy of FATL must be verified. Therefore, we present a protocol for the MASET-TLE trial. This is the first study to evaluate the clinical outcomes of FATL as a novel surgical approach for TLE.

STUDY GOALS AND OBJECTIVES

Hypothesis

As a minimally invasive procedure, the overall hypothesis is that patients with TLE will benefit from FATL, with seizure control and neuropsychological outcomes no less than standard ATL whereas complications and cosmetic appearance superior to ATL. Therefore, the goal of this study was to measure the surgical technique, safety, and efficacy of FATL compared to ATL at the department of neurosurgery in our hospital.

Primary Objective

- Minimally invasive outcomes: surgery duration, intraoperative blood loss, length of skin incision, bone flap size, and postoperative hospital stay.
- Complications and cosmetic appearance of the wound at the 1-year follow-up after epilepsy surgery.

Secondary Objectives

- Seizure outcomes were categorized according to the Engel and International League Against Epilepsy (ILAE) classifications.¹⁸ The actuarial seizure outcomes over time were evaluated using the Kaplan–Meier analysis.

- Quality of life is evaluated by the epilepsy-specific Quality of Life in Epilepsy Inventory-89 (QOLIE-89; range of scores, 0 to 100, with higher scores indicating better quality of life).¹⁹
- Neuropsychological outcomes were assessed according to the consensus reported by Brissart.²⁰

STUDY DESIGN

MISSET-TLE is a single-center, prospective, single-blinded, double-arm, randomized controlled trial. A total of 120 patients are planned to be recruited (60 patients per group). The anticipated completion date will be in July 2024. SPIRIT checklist is used when writing our report.²¹

Inclusion/Exclusion Criteria

Inclusion Criteria

- male or female aged between 18 and 60 years.
- drug-resistant TLE, with remaining seizures after two or more tolerated and appropriately chosen antiepileptic drugs for at least 1 year.
- monthly or more frequent seizures during the preceding year prior to the trial.
- full-scale intelligence quotient (IQ) more than 70, able to understand and complete the trial.
- signed informed consent.
- good compliance, at least 12-month follow-up after surgery.

Exclusion Criteria

- tumor in the temporal lobe.
- extratemporal epilepsy and temporal plus epilepsy.
- drug-responsive epilepsy, seizure freedom with current drugs in the past year.
- pseudoseizures.
- seizures arising from the bilateral temporal lobes.
- significant comorbidities including progressive neurological disorders, active psychosis, and drug abuse.
- a full-scale IQ lower than 70, inability to complete tests.

- previous epilepsy surgery.
- poor compliance and inadequate follow-up.

METHODOLOGY

Screening and Enrollment

Pre-screening will be conducted for known or referred patients with TLE who may be eligible for the trial. All potential subjects will undergo a detailed screening visit at our center. Presurgical evaluations include seizure semiology, electroencephalography, imageology, and neuropsychology. Long-term video scalp electroencephalogram (EEG) with bilateral sphenoid electrodes in the standard 10–20 system will be used to monitor each patient for more than 24 hours. The 3-Tesla magnetic resonance imaging (MRI) epilepsy protocol includes three-dimensional (axial, coronal, and sagittal) scanning of T1-weighted, T2-weighted, and fluid-attenuated inversion recovery (FLAIR) sequences with a slice thickness of 1 mm without an intervening gap. If epileptiform discharges arising from bilateral temporal lobes in scalp EEG, MRI, and EEG are inconsistent, intracranial EEG was performed for the lateralization of the epileptic focus. Positron emission computed tomography (PET) will be performed to evaluate the metabolism of the temporal lobe, especially in patients with negative MRI findings. Then, MRI and PET will be processed and merged using 3D slicer software (ver. 4.7).

Each patient case will be discussed by a multidisciplinary epilepsy team consisting of neurologists, neurosurgeons, neuroradiologists, and nuclear medicine specialists to confirm eligible patients. In addition, the assessments of neuropsychologists and psychiatrists will be taken into consideration before the trial to evaluate coexisting psychiatric conditions. Above evaluations will serve as baseline results. Flow chart of the study is showed in Figure 1. Recruitment advertisement of trial is issued on the Internet and introduced to regional epilepsy centers and associations in Northwest China, for securing the number of eligible subjects.

Randomization and Blinding

Patients will be assigned with computer-generated random numbers by an independent statistician. Randomization is stratified by sex, with separate permuted blocks for each sex. Allocations are concealed until participants' eligibility and identities are confirmed. Allocations are also sequentially numbered in a 1:1 ratio to either receive FATL (experimental group) or

ATL (control group). Assessors evaluating the outcomes will be blinded to treatment throughout the study. Blinding is maintained by having patients wear large hats during reviews to obscure skin incision and providing patients strict instructions not to reveal their treatment arm.

Surgical Intervention

FATL

Patients will be placed in the supine position with their head contralaterally rotated by 30°. The 3D model of the incision and bone flap will be printed prior to the surgery using the slicer software based on the MRI data. A slightly curve incision with a length of approximately 6 cm in the temporal region beginning from the zygomatic arch will be marked (Figure 2A). A temporal craniotomy via a small bone window with a diameter of about 3 cm will be performed (Figure 2B and C). From the temporal pole approximately 4-5 cm posteriorly, the temporal horn is opened by dissecting the middle temporal gyrus. The head of the temporal horn will be exposed. The amygdala will be resected. Then, the parahippocampal gyrus and the hippocampus will be resected en bloc. Temporal lobotomy is easy because of the large view following the removal of the mesial structures (Figure 2D and E). The lateral posterior temporal lobotomy was no more than 5 cm from the temporal pole. Finally, the temporal stem was divided to isolate the superior temporal gyrus.

ATL

Patients will be placed in the supine position with their head contralaterally rotated by 30°. A large frontotemporal craniotomy will be performed. A question mark-shaped incision with a length of 20-25 cm in the frontotemporal region beginning from the zygomatic arch will be marked (Figure 2F). The size of the bone flap is approximately 5 × 7 cm for exposure of the lateral temporal lobe (Figure 2G and H). ATL consists of a standard protocol including en bloc resection of the anterior 5 cm of the lateral temporal lobe, followed by the removal of mesial structures including the amygdala, parahippocampal gyrus, and the hippocampus (Figure 2I and J).

DISCUSSION

Currently, there is still no consensus on the optimal surgical approach for TLE,¹⁴ and surgical approaches are often based on the neurosurgeon's experience and preference. The surgical goal for TLE is to perform a more extensive resection under the premise of minimal functional deficits to achieve maximum seizure control.²² ATL involves removing 4–6 cm of the anterior temporal lobe, including the amygdala and hippocampus.⁴ With the advances and understanding of microsurgical neuroanatomy and surgical techniques, minimally invasive surgery is a trend for less-invasive procedures, fewer complications, and better neuropsychological outcomes.

FATL is more likely to be accepted by patients compared with ATL. As a new surgical approach, FATL has several advantages. Firstly, amygdalohippocampectomy provides greater view for facilitating the temporal lobotomy, and guaranteeing the complete disconnection and isolation of the temporal lobe. Secondly, temporal lobotomy, disconnecting the lateral temporal cortex, avoids potential complications related to larger cavity volume after parenchymal defect in ATL. Thirdly, faster recovery is obtained due to a reduction in surgery duration, blood loss, complications, and hospital stay after this minimally invasive surgery. Finally, better cosmetic appearance of the wound is obtained because of minicraniotomy. Scar wound and muscular atrophy are common in patients with ATL by large frontotemporal craniotomy. We hypothesize that FATL is a less-invasive, safe and effective therapy for TLE. In this trial, we will compare the clinical outcomes of FATL for TLE with ATL.

TRIAL STATUS

Patient recruitment began in September 2021. This study is expected to be completed by July 2024. Final data analyses will be performed, and final reports will be published over the following year.

SAFETY CONSIDERATIONS

Complications, such as any deviation from the normal postoperative course, are defined by the criteria and definitions for ATL-associated complications reported by Brotis.²³ These include surgical-site infection, hemorrhage, neurological deficits, cerebrospinal fluid leak, subdural fluid collection, hydrocephalus, and medical complications (less likely, e.g., deep vein thrombosis, urinary tract infection, acute kidney/lung disorders, respiratory distress or failure,

etc.). The severity of a complication is graded as minor if it resolves within 3 months, and major if it lasts longer than 3 months and affects the activities of daily living.²⁴

FOLLOW-UP

After surgery, patients continue to take antiepileptic drugs, and changes are made by clinicians as necessary to manage seizures. Study scheme and follow up are showed in Figure 3. Patients will be followed up for at least one year. Patients are seen in the outpatient clinic at 1 month after surgery, then every 3 months for 1 year, and subsequently at yearly intervals. Patients will be required to write detailed descriptions of all seizure events in their monthly seizure diaries. EEG and neuropsychological scales will be examined at each follow-up. MRI will be performed 3 months after surgery to evaluate the extent of resection. Antiepileptic drugs will be tapered and discontinued in the period of 3–6 months if patients remain seizure-free at 1 year after surgery. Antiepileptic drugs will be administered again when patients experience seizure recurrence.

DATA MANAGEMENT AND STATISTICAL ANALYSIS

Final data capture and storage will be performed via electronic case report forms (eCRF) using an electronic database that is fully compliant with privacy regulations. In addition to eCRFs, data will be retained along with relevant supporting documentation, such as scans, progress notes, nursing notes, blood work, and pathology reports. All records and documents pertaining to the study will be retained by all the participating study trial sites for at least 10 years from the completion of the study, and will be available for inspection by the research ethics board, quality assurance, and other regulatory bodies. Hard copy study files (consent forms, questionnaires, and coordinator source notes from participant research charts) will be kept secured with the Department of Neurosurgery. All computerized files will be password-protected.

Statistical Considerations

Based on the mean surgery duration in our center (3.4 h in the ATL group vs. 3.0 h in the FATL group), we needed to enroll 50 patients per group in order to detect a statistical difference with 90 percent power at a two-sided significance level of 0.05. Anticipating up to a 20% attrition rate, there are 120 patients recruited.

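### Assessor blinding rests on hiding the incision, so it cannot hold for the primary outcome that rates how that wound looks

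*Combined protocol and SAP*

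**What the plan says.** Randomization and Blinding makes a general promise: "Assessors evaluating the outcomes will be blinded to treatment throughout the study". No outcome is excepted. Two measures support it. One is the hat: "Blinding is maintained by having patients wear large hats during reviews to obscure skin incision". The other is that participants are told to keep their allocation to themselves. Study Design calls the trial single-blinded.

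The list of primary outcomes in the abstract closes with "cosmetic appearance of the wound, and complications at the 1-year follow-up after surgery". Primary Objective repeats this as "Complications and cosmetic appearance of the wound at the 1-year follow-up after epilepsy surgery". The Hypothesis section gives the expected direction: "complications and cosmetic appearance superior to ATL".

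Surgical Intervention describes the two scars. For FATL it is "A slightly curve incision with a length of approximately 6 cm in the temporal region"; for ATL it is "A question mark-shaped incision with a length of 20-25 cm in the frontotemporal region".

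Project Management lists three outcome assessors and does not divide the outcomes among them. Follow-up schedules EEG and neuropsychological scales at every visit and refers to Figure 3 for the scheme; that figure was not available for this review. The available text names no cosmetic scale, wound rater, photographic reading or patient self-rating, and gives no order of assessment within a visit.

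**The concern.** The feature that the hat is meant to hide is the feature that a primary outcome asks someone to look at. An assessor cannot both stay blinded by the hat and rate the wound. As written, the protocol would lead to a cosmetic result being reported as assessor-blinded when it was not.

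This matters because, with no scale named, the rating is left to judgement, and the investigators have said in advance which arm they expect to do better. The Discussion goes further and treats the better appearance after the small craniotomy as an advantage already in hand. A rater who shares that view and can see the arm may score it generously. The trial is intended to supply level 1 evidence, so readers will rely on how its outcomes are described as having been measured.

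**Working it through.** The plan gives no figure to reproduce on this point. The check sets the sections side by side, with three small pieces of arithmetic.

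1. **Scope of the promise** (Randomization and Blinding). It covers assessors of the outcomes, for the whole study, without exception. By choosing a hat, the protocol itself treats the incision as revealing the arm.

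2. **Outcome affected** (abstract, Methods; Primary Objective). The primary outcomes are surgery duration, blood loss, incision length, bone flap size, postoperative stay, cosmetic appearance and complications, which makes 7. Cosmetic appearance is 1 of these 7. Incision length and bone flap size are operative measures; they are inherently unblinded, and recording them need not unblind a clinic assessor.

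3. **Can the scars be told apart?** (Surgical Intervention). Ratio of planned lengths, ATL to FATL: 20 / 6 = 3.3 up to 25 / 6 = 4.2. Shape and site differ too. Anyone who sees the scar can very probably name the arm.

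4. **Possible raters.**
   - Assessor, hat on: the wound cannot be rated.
   - Assessor, hat off: the wound can be rated, but the arm is visible.
   - Assessor, from photographs: length and shape still show the arm, so photographs alone do not restore blinding.
   - Patient: the hat rule is not contradicted. However, the text describes no blinding of patients, and the instruction not to reveal the arm presumes that they know it. The rating is probably still unblinded.

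   None of these options gives a blinded cosmetic rating.

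5. **Patients concerned** (Statistical Considerations). 120 are recruited with up to 20% attrition: 120 × (1 − 0.20) = 96, so 96 to 120 patients at 1 year.

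6. **Reach beyond cosmesis.** The wound is a 1-year outcome, so the cosmetic rating itself cannot unblind earlier visits. At 1 year, seizure class and neuropsychology are exposed only if the same person rates them at or after the wound rating. Complications are less exposed: Safety Considerations and its continuation grade severity by whether the problem resolves within 3 months, so early events would usually be gradable long before the 1-year wound rating.

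7. **A separate route to the scar** (Follow-up). EEG is done at each follow-up. If this is scalp EEG, the hat would presumably come off each time. Whether an outcome assessor is present is not stated.

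**The case against.** The strongest reply is that a scar's appearance cannot be blinded when the scar is the treatment difference. Scoring a longer scar worse may be the true effect rather than bias, and the sample size rests on surgery duration, not cosmesis. This stands in part: no change to the plan would blind the rating. It does not rescue the wording, because the protocol claims blinding for every outcome and draws no such exception.

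A second reply is that the patient may be the rater, or that Figure 3 may settle rater and order. Neither can be excluded. Patient rating would remove the clash with the hat but would probably not make the outcome blinded.

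Three stronger readings are tempting and are not supported.

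- A reader might infer that complications, seizure class and neuropsychology are all unblinded. That needs the wound rater also to make those ratings at or after seeing the scar, or an assessor to be present when the scalp is uncovered. The available text states neither.
- A reader might infer that a cosmetic advantage for FATL would be an artefact. A real difference is plausible given the two incisions, so bias is more likely to inflate the estimate than to create it.
- A reader might take the smallest difference that reaches P < 0.05 at these sample sizes as a measure of the bias. That cut-off follows from the number of patients for any outcome and says nothing about how far a rater who sees the scar would drift.

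**Conclusion.** The point holds for one of the seven primary outcomes. For cosmetic appearance at 1 year, the stated assessor blinding cannot be kept by any assessor who does the rating. This is an error in what the plan claims, not merely an omitted detail. The expected direction of any bias is towards FATL; its size cannot be computed from the documents.

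The conclusion assumes that the rating involves judgement, since no scale is named, and that nothing in the figures not shown assigns the rating differently. The point about patient raters assumes that patients know their arm. Spill-over to other 1-year ratings remains conditional on who rates what and in which order; it is weakest for complications. The point should be corrected, but it does not undermine the trial as a whole.

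**What to change.** In Randomization and Blinding, state who rates the wound, and report cosmetic appearance and the operative measures as not assessor-blinded.

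At the 1-year visit, do one of two things:

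- keep the hat on until the other ratings are entered and locked in the eCRF, then rate the wound last; or
- give the wound to one of the three existing assessors who does not make that patient's other ratings.

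In either case, anyone who has seen the scar makes no later blinded rating for that patient. Keep outcome assessors away from every step that uncovers the scalp, including the EEG at each follow-up.

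Then claim assessor blinding only for outcomes whose raters have not seen the scar. The 1-year reordering should not be presented as securing blinding for the whole study, because it does nothing about exposure at earlier visits.

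The cost is slightly tighter visit scheduling and a cosmetic outcome reported as open-label. Eligibility, treatment, sample size and visit dates do not change. Recruitment began in September 2021, so the rater and order rules can apply to the 1-year visits still to come, and the corrected description of blinding to all reports.
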